#### **4.3 *Subject Recruitment and Screening***

It is anticipated that 120 participants can be recruited within 48 months based on prior rates of enrollment for alcohol studies conducted by the proposed study team and the awareness that the current proposal will study individuals over a longer period of time and needs to recruit a minimum number of individuals with heavy drinking and with high anxiety. In our recently completed placebo study of baclofen we were able to recruit 80 subjects over 19 months with 75% trial retention. Retention is an important objective of the trial with our target being a minimum of 75% of subjects completing the trial. Medical Management and the regular meetings with our research coordinator during study visits have proven useful in encouraging retention and compliance with medication and we have averaged 75-85% retention for most trials.

Potential participants will be recruited from the Raleigh, Durham, and Chapel Hill areas by screening patients at Freedom House and via advertising and referrals. Freedom House is a local publically funded detoxification center. Approximately 350 alcohol dependent individuals per year are admitted to Freedom House. These individuals have been screened to minimize risk of more serious withdrawal problems such as DTs or seizures and individuals with serious psychiatric problems such as suicidal behavior or psychosis or serious medical problems that require acute care are not admitted. Patients at Freedom House receive medical or social detoxification depending on symptom severity. A CIWA-Ar driven protocol using lorazepam has been utilized there. The average length of stay at Freedom House is 4 days. This population represents treatment seeking individuals who are more likely to have higher levels of physical dependence than our traditional trial population recruited by advertising. This is a very important point as this population may be the one that responds best to baclofen (see Leggio et al, 2010).

Individuals at Freedom House will be screened in person whereas those who respond to advertisements will have a preliminary telephone screening conducted by the study coordinator. Individuals who appear eligible, as determined by the investigative team, will be scheduled to come to the UNC Hospitals for more comprehensive screening. Prior to full screening, individuals will read and sign the informed consent and be given a copy for their records.

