To move the treatment of AD forward there is a compelling need to find new medications that are both effective and well tolerated. Furthermore, it would be very helpful for clinicians to have access to medications that target not only drinking behavior but also other aspects of the AD syndrome such as anxiety that are commonly found in patients with AD and contribute to relapse (Kushner et al, 2000). Achieving the latter goal would represent a step towards personalized medicine in AD.

[figure not shown]
A body of preclinical and clinical evidence has arisen over the past 30 years that indicates that the GABAB agonist baclofen may have therapeutic value in AD. Baclofen has advantages as a possible therapeutic innovation for AD as it is approved by the FDA and has an extensive track record in human use. Its safety profile is quite good--even with intentional overdoses most patients fully recover (see Wall et al, 2006). The drug is rapidly absorbed after oral administration and is widely distributed throughout the body. Biotransformation is low and the drug is predominantly excreted in the unchanged form by the kidneys, which makes it safe to use in AD patients with compromised liver function (Addolorato et al., 2007). Another beneficial property of baclofen is that tolerance does not seem to occur to any significant degree — baclofen retains its therapeutic effects even after many years of continued use (Gaillard 1977).

Therefore, if baclofen does indeed demonstrate efficacy in AD, it would provide clinicians with another readily available tool to treat the AD patient. Furthermore, there is solid preclinical and clinical

evidence that baclofen also can target anxiety symptoms in AD and may even reduce the likelihood of their development (see Knapp et al, 2007). If true, baclofen could be of considerable value as a means to help manage anxiety symptoms in the AD patient—symptoms which can be difficult to manage and which can trigger relapse. Baclofen is particularly interesting in this regard as, unlike other anxiolytics such as the benzodiazepines, it does not have clear addictive properties and appears relatively safe when combined with alcohol. The purpose of the present proposal is to investigate the efficacy and tolerability of baclofen for alcohol dependence with attention to several key issues including baclofen dose, severity of dependence and severity of coexisting anxiety symptoms.

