### 3 Study Design

#### 3.1 General Design

This is a Phase II, randomized, double blind, placebo controlled trial of baclofen for the treatment of alcohol dependence. The study proposes to enroll 120 men and women with AD in a randomized, placebo-controlled trial to include at least 60 individuals with high levels of drinking ( $\geq 14$  drinks/drinking day for men;  $\geq 10$  drinks/drinking day for women) with randomization to baclofen or placebo balanced for this variable. Baclofen will be titrated to 10 mg t.i.d over 3 days and to 30 mg t.i.d over 12 days and maintained at that level for 12 weeks and then down-titrated for a total study time of 16 weeks. Medical Management will be provided to encourage progress towards drinking goals and to enhance retention and compliance. Drinking patterns, anxiety levels, sleep patterns, craving for alcohol, gamma-glutamyl transferase (GGT) and carbohydrate deficient transferrin (CDT) will be assessed.

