### 4 Subject Selection and Withdrawal

#### 4.1 Inclusion Criteria

1. Men and women between the ages of 18 and 65 meeting DSM-IV criteria for current alcohol dependence.
2. More than 14 drinks (women) or 21 drinks (men) per week including at least 2 heavy drinking days (men  $> 5$  drinks/day; women  $> 4$  drinks/day) per week in the 30-day period prior to screening. In addition we will recruit 50% of individuals who have a mean of  $\geq 14$  drinks/drinking day (men) or  $\geq 10$  drinks/drinking day (women) in the 30 days prior to screening.
3. Ability to understand and sign written informed consent.
4. Must have a 0.0 gms/dl breathalyzer reading on the day of screening and 0.0 gms/dl on the day of randomization.
5. Express a desire to achieve abstinence or to greatly reduce alcohol consumption
6. Must have a stable residence and be able to identify an individual who could contact participant if needed.

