#### 4.2 Exclusion Criteria

1. Clinically significant medical disease that might interfere with the evaluation of the study medication or present a safety concern (e.g., renal insufficiency, cirrhosis, unstable hypertension, diabetes mellitus, seizure disorder). Clinically significant psychiatric illness including any psychotic disorder, bipolar disorder, severe depression, or suicidal ideation.
2. Other substance abuse or dependence disorder other than nicotine or alcohol or cannabis abuse. Occasional use of cocaine is acceptable.
3. Concurrent use of any psychotropic medication including antidepressants, mood stabilizers, antipsychotics, anxiolytics, stimulants, or hypnotics with the exception of stable doses of antidepressants for one month. Concurrent use of anticonvulsants, insulin, or oral hypoglycemics.
4. Prior history of adverse reaction to baclofen.
5. Estimated Glomerular Filtration Rate  $<$  age norm.
6. AST, or ALT  $>$  5 times ULN or bilirubin  $>$  1.5 X ULN.
7. Positive urine toxicology screen with the exception of cannabis. Individuals with positive cannabis screens will be excluded only if they have a history of cannabis dependence.

8. Pregnant women and women of childbearing potential who do not practice a medically acceptable form of birth control (oral or depot contraceptive, or barrier methods such as diaphragm or condom with spermicidal).
9. Women who are breastfeeding.
10. Individuals requiring inpatient treatment or more intense outpatient treatment for their alcohol dependence.
11. Participation in any clinical trial within the past 60 days.
12. Court-mandated participation in alcohol treatment or pending incarceration.

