### **5.3 Method for Assigning Subjects to Treatment Groups**

Randomization blocks will be prepared by the statistician and provided to the Investigational Drug Services. A minimization random assignment procedure will be used to match subjects on the key moderator (DDD) (< 14 DDD or  $\geq 14$  DDD for men and <10 DDD or  $\geq 10$  DDD for women. Randomization will be linked to sequential study number which subjects receive as they enroll in the study.

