## **5.6 *Blinding of Study Drug (if applicable)***

The study biostatistician, will prepare the randomization schedule and include blocking by high/low DDD ( $\geq 14$  for men and  $\geq 10$  DDD for women) and by gender. The randomization schedule will be given to IDS personnel; investigators will not have access to this information. If a medical or other emergency necessitates breaking the blind, IDS personnel will provide the identity of the medication to the PI or another medical study team member.

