**Treatment of Missing Data:** With repeated assessments, missing data/attrition is inevitable, but the key thing is that the specified contrasts are not affected due to the presence/absence of data. We will use pattern-mixture models to assess if there is bias due to drop out or missing data (Hedeker and Gibbons, 1997). To address missing data in the survival models, Dupuy and Mesbah(2004) considered jointly modeling time to event data with missing covariate data in order to assess if the missing data is ignorable or non-ignorable. These approaches will be implemented to the fitted cox model. Days in treatment may directly impact the treatment comparison for assessing differences. To control for this potential issue, we will also assess Marginal Structural Cox Regression models (Xiao et al., 2010).

**Adjustment for Covariates:** All modeling approaches allow for the inclusion of covariates. We will include any measures differing at baseline or important potentially confounding measures (i.e. gender, race) in our models to disentangle the intervention effect from these measures

**Specific Aim 2. To test the hypothesis that a history of heavy drinking as assessed by average drinks/drinking day in the 30 days preceding screening predicts baclofen response in alcohol dependence.**

We will include the pre-treatment HDD measure in all models above to examine its predictive merit, as well as its potential moderating impact of the baclofen effect. Moderation effect will be assessed by including the interaction of pre-treatment HDD with the treatment assignment. We will treat pre-

treatment HDD as a continuous measure. We will use mean profile plots based on quartiles of HDD to assess if the continuous measure has a linear, piecewise linear, or curvilinear effect. .

**Specific Aim 3. To test the hypothesis that baclofen, 30 mg/d and 90 mg/d, is superior to placebo in reducing anxiety in alcohol dependence.**

Our analytic procedure is as described in Aim 1 using mixed effects model to account for the repeated measures over time, while contrasting the mean intervention effect as well as assessing the potential moderation effect of pre-treatment HDD.

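### A minimum number of participants with high anxiety is announced but never implemented, and the Aim 3 model has no pre-specified baseline anxiety term

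*Combined protocol and SAP*

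**What the plan says.** Section 4.3, on the 48-month recruitment estimate, says the study "needs to recruit a minimum number of individuals with heavy drinking and with high anxiety". Section 6 (Recruitment and Retention) repeats it. Neither gives a number or defines high anxiety. Section 1.1 lists among the key issues "severity of dependence and severity of coexisting anxiety symptoms".

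Elsewhere only drinking is acted on:
- Section 3.1 plans 120 participants, "to include at least 60 individuals with high levels of drinking".
- Section 4.1 sets the matching quota: "In addition we will recruit 50% of individuals who have a mean of" at least 14 (men) or 10 (women) drinks per drinking day.
- Section 5.3 allocates on drinks per drinking day: "A minimization random assignment procedure will be used to match subjects on the key moderator (DDD". Section 5.6 adds blocking "and by gender. The randomization schedule will be given to IDS personnel".
- Section 7.1 powers one moderator, heavy drinking.

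The formal anxiety objective in Section 2 concerns anxiety in alcohol dependence generally. Section 7.2 (Aim 3) uses the Aim 1 mixed model, "contrasting the mean intervention effect as well as assessing the potential moderation effect of pre-treatment HDD". The covariate paragraph admits measures that differ at baseline and important potential confounders, with gender and race as its examples. The schedule of assessments collects STAI-state at screening, at the initial visit and at every later visit.

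**The concern.** Two things are at stake.

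First, the protocol states a recruitment requirement that nobody can meet or audit, because it has no threshold and no count. A reader of the eventual report could believe the sample was enriched for anxiety when nothing in the design does that.

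Second, anxiety is the Aim 3 outcome and its pre-treatment value is recorded, yet the model does not commit to using it. Under the covariate rule, baseline STAI-state enters if the arms look different or if someone later classes it as a confounder. The model then depends on the data, by a criterion for differing that the plan does not define. If the arms look alike, the precision from adjusting for the outcome's own baseline is lost. The rationale in Section 1.4, that baclofen may be especially useful in patients with anxiety symptoms, has no planned analysis. Any later look at it would involve a choice of cut-off or model made after seeing the data.

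**Working it through.** **Step 1. The two halves of the recruitment sentence compared.**

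| Element | Heavy drinking | High anxiety |
|---|---|---|
| Definition | at least 14 (men) or 10 (women) drinks per drinking day (3.1, 4.1) | none |
| Number or share | at least 60 of 120; 50% (3.1, 4.1) | none |
| Allocation factor | yes (5.3, 5.4, 5.6, 6) | none; 5.6 adds only gender |
| Moderator in the model | yes (7.2, Aims 2 and 3) | none |
| Power for moderation | 86.7%; 80.2% with attrition (7.1, Aim 2) | none |

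**Step 2. What the Aim 3 power covers.** Section 7.1 gives 82.2% at effect size 0.5, and 82.0% at 0.55 with 16.2% attrition. Alpha and sidedness are not stated.
- Placebo 40 versus pooled baclofen 80: noncentrality = 0.5 / √(1/40 + 1/80) = 0.5 / 0.1936 = 2.58 on 118 df. A one-sided 5% t test gives 82.2%, which reproduces the plan. A two-sided 5% test gives 72.6%.
- With attrition, 33 versus 66: 0.55 / √(1/33 + 1/66) = 0.55 / 0.2132 = 2.58. One-sided 5% gives 82.0%, which also reproduces.

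The stated power is therefore for a whole-sample comparison with no baseline adjustment. No anxious subgroup and no anxiety interaction is included.

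**Step 3. Precision from adjusting for baseline STAI-state.** The documents give no correlation r between baseline and on-treatment scores; 0.4 to 0.6 is assumed. Residual variance after adjustment is (1 − r²) times the unadjusted variance.
- r = 0.4: 1 − 0.16 = 0.84, a 16% reduction; standard error × √0.84 = 0.92; equivalent unadjusted sample 120 / 0.84 ≈ 143.
- r = 0.6: 1 − 0.36 = 0.64, a 36% reduction; standard error × √0.64 = 0.80; equivalent unadjusted sample 120 / 0.64 ≈ 188.

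The plan does not say whether the outcome is the score itself or its change. For a change score with equal variances, the ratio is (1 − r²) / (2 − 2r) = (1 + r) / 2, which is 0.70 at r = 0.4 and 0.80 at r = 0.6. Adjustment still removes 30% to 20%. If the initial-visit score were modelled as one of the repeated outcomes, part of this gain would already be captured; the plan does not say that either.

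**Step 4. What an anxiety moderator could show.** The documents give no share of highly anxious participants, so a range is assumed, with equal shares per arm, no attrition and two-sided 5%. With n_h = 40 × share and n_l = 40 − n_h, the interaction standard error (in SD units) is √(1.5/n_h + 1.5/n_l). At a 50% share it is √(1.5/20 + 1.5/20) = 0.387, and 1.2 / 0.387 = 3.10, giving 87%, the Aim 2 figure.

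| Assumed share (n of 120) | Subgroup power, d = 0.5 | Interaction of 0.5 SD | Interaction of 1.2 SD |
|---|---|---|---|
| 10% (12) | 11% | 12% | 45% |
| 23.5% (28) | 23% | 19% | 74% |
| 33% (40) | 31% | 23% | 83% |
| 50% (60) | 44% | 25% | 87% |

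The 23.5% is the twelve-month DSM-IV anxiety-disorder rate in Section 1.4. It is not a share of high STAI scores and is only one point in the range. The 1.2 SD is borrowed from the drinking moderator, and nothing supports it for anxiety. A high/low split stands in for the continuous score, whose slope is not given.

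**The case against.** The sentence in Sections 4.3 and 6 explains a recruitment timeline; it is not an eligibility rule, and removing a few words resolves the contradiction. That is right, and it is the simplest remedy. It does not supply the missing baseline term.

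The formal objective concerns anxiety in all participants. That stands. A reader might infer that the trial cannot answer its anxiety question. The documents do not support this: Section 2 sets a whole-sample objective, the Aim 3 comparison of arms is valid with or without a quota, and because STAI-state is collected an interaction can still be fitted.

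A reader might also infer that anxious patients are kept out, because Section 4.2 excludes "Concurrent use of any psychotropic medication including antidepressants, mood stabilizers, antipsychotics, anxiolytics, stimulants, or hypnotics". That criterion exempts stable antidepressants, no exclusion names anxiety disorders, and barring anxiolytics protects an anxiety endpoint. Nor do the documents show that an unselected sample has too little room to improve: Table 1 of Section 1.4 reports anxiety reductions in two double-blind trials (n = 39 and n = 80) and describes no selection for anxiety.

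A further temptation is to demand an anxiety quota or a second allocation factor. Neither follows. Chance imbalance on an unbalanced factor is ordinary and covariate adjustment deals with it. A 50% quota would still give only 44% subgroup power at d = 0.5, while adding screening burden. These are the investigators' trade-offs.

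Finally, the covariate rule would pick up a visible baseline difference. It would, but only conditionally, and it gains nothing when the arms look alike.

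**Conclusion.** The point holds as an inconsistency and a missed, cost-free gain. The stated high-anxiety minimum has no cut-off, number, quota, allocation factor or analysis term behind it. The whole-sample Aim 3 test is valid but unnecessarily imprecise: pre-specified adjustment would cut residual variance by about 16% to 36% compared with an analysis that ignores baseline, if r lies between 0.4 and 0.6. That correlation is an assumption; the documents give none. Moderation by anxiety severity is not planned. Under the assumed shares, power for a 0.5 SD interaction would be 12% to 25%, so it can only be exploratory. The primary aim is not touched.

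**What to change.** 1. In Section 7.2, Aim 3, pre-specify the initial-visit STAI-state score, as a continuous covariate, for all participants whether or not the arms differ on it.
2. In the same place, pre-specify continuous baseline STAI-state by treatment as a secondary, exploratory moderator alongside the drinking moderator. Leave the order of the aims unchanged and state that the interaction is not powered.
3. Reconcile Sections 4.3 and 6 with Section 4.1. The simplest way is to delete the reference to high anxiety from both recruitment paragraphs and to describe the Aim 3 conclusion as applying to an alcohol-dependent sample not selected for anxiety. If the investigators do want a minimum, Section 4.1 must give its definition and number.

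The cost is wording. The score is already collected at the initial visit, so there are no new participants, visits or questionnaires, and allocation is unchanged. The covariate uses one degree of freedom. The exploratory term adds a result that must be reported as such.

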#### **4.4 *Early Withdrawal of Subjects***

Subjects can withdraw from this study at any time, without penalty. The investigators also have the right to stop subject's participation at any time.

A subject who experiences a serious adverse event thought to be possibly or probably related to study medication will have their medication tapered and stopped. It is preferable to taper baclofen then stopping it abruptly. If a subject is having moderate side-effects the medication can be reduced and side-effects monitored. If a subject continues to have side-effects the medication may be tapered and stopped. We will make every effort to maintain subjects in the trial as long as safety is adhered to. If a subject does not comply with medication instructions we may need to discontinue

medication for safety purposes. We will follow subjects off medication to collect outcome data such as drinking behavior.

#### **4.4.1 Data Collection and Follow-up for Withdrawn Subjects**

Any data collected up to the time of withdrawal will be kept, as well as any follow-up information related to subject safety.

### **5 Study Drug**

#### **5.1 Description**

Lioresal, baclofen USP, is a muscle relaxant and antispastic, available as 10-mg and 20-mg tablets for oral administration. Baclofen USP is a white to off-white, odorless or practically odorless crystalline powder, with a molecular weight of 213.66. It is slightly soluble in water, very slightly soluble in methanol, and insoluble in chloroform.

Inactive Ingredients. Cellulose compounds, magnesium stearate, povidone, and starch.

The precise mechanism of action of Lioresal is not fully known. Lioresal is capable of inhibiting both monosynaptic and polysynaptic reflexes at the spinal level, possibly by hyperpolarization of afferent terminals, although actions at supraspinal sites may also occur and contribute to its clinical effect. Although Lioresal is an analog of the putative inhibitory neurotransmitter gamma-aminobutyric acid (GABA), there is no conclusive evidence that actions on GABA systems are involved in the production of its clinical effects. In studies with animals, Lioresal has been shown to have general CNS depressant properties as indicated by the production of sedation with tolerance, somnolence, ataxia, and respiratory and cardiovascular depression. Lioresal is rapidly and extensively absorbed and eliminated. Absorption may be dose-dependent, being reduced with increasing doses. Lioresal is excreted primarily by the kidney in unchanged form and there is relatively large inter subject variation in absorption and/or elimination.

#### **5.2 Treatment Regimen**

It is important to uptitrate and downtitrate the dose of baclofen to minimize side-effects. We will parallel the titration schedule used by Franklin et al (2009) in their study of 20 mg of baclofen given four times per day. In the latter study, baclofen was well tolerated without significant differences between baclofen and placebo groups—for the chief side-effect of sedation, the baclofen group had 20 mild, 4 moderate and 0 severe reports of sedation compared to 4 reports of mild sedation and 0 reports of either moderate or severe sedation with placebo (Franklin et al, 2009). Our titration schedule for the 90 mg/d dose is shown in Table 1. The 30 mg/d arm will reach 30 mg/d at day 3 and titrate down starting at day 101.

